2 SYNOPSIS

Protocol Number	PG-001
Protocol Title	Safety and Effectiveness Evaluation of the Peregrine™ Drivable ENT Scope for Office Endoscopy of the Paranasal Sinuses in Patients who underwent ESS
Participating Centers	Emory University, Atlanta, GA
Clinical Phase	Open, single-center, prospective
Investigational Study Device	Peregrine™ Drivable ENT Scope, by 3NT Medical
Study Procedures	
Up to 30 Patients, out of which are at least 10 samples per each of the frontal, maxillary and sphenoid sinuses, who have had prior ESS and are scheduled for nasal endoscopy in the office as part of a routine post-operative office visit or due to recurrence of symptoms, will be evaluated with Peregrine Endoscope. The patients will attend the following visits:
 
 1. Visit 1: Screening and Enrollment – as part of a regular office visit 2. Visit 2: Sinonasal endoscopy – evaluation with Peregrine and standard endoscopes 
Visits 1 and 2 can be combined into a single visit.

Study Population	Patients who have had prior ESS
Study Purpose	To assess the safety and effectiveness of Peregrine endoscope in patients in the office setting in terms of access into and visualization of the paranasal sinus anatomy, image quality, patient tolerability and clinical utility.
Study Endpoints	
Primary – Performance and Safety Endpoints:
 
 • To compare visualization success rates of the paranasal sinus anatomy by Peregrine and by a standard endoscope used in the office setting. • Device related adverse events 
Secondary – Performance Endpoints:
 
 • To assess the adequacy of the image quality of Peregrine for endoscopy procedures in the office. • To evaluate patient tolerability and pain • To evaluate the impact of extended visualization by Peregrine on clinical workflow

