4.3 Study End Points

Primary - Safety

All adverse device effects will be captured and summarized as defined in **Section-8**. Adverse device effects (type, frequency, severity) are expected to be similar to those reported in the literature for Nasal Endoscopy (section 8).

For this study, the Safety comparison with the data of Nasal Endoscopy reported in the literature will be descriptive with no statistical endpoints.

Primary – Performance

Evaluation of ability of Peregrine and the comparison endoscope to access and visualize sinus anatomy at the following landmarks:

- Maxillary (ostium, anterior wall, lateral aspect, floor)
- Frontal (ostium, posterior wall, anterior wall, lateral recess)
- Sphenoid (ostium, sella, floor, lateral recess)

Subjects will be evaluated with:

- a. Mandatory – Peregrine Endoscope (the study device)
- b. Mandatory – A Standard 30° 4mm endoscope
- c. Optional – A Standard 70° 4mm endoscope
- d. Optional – A standard Flexible Endoscope

- Visualization success rates, calculated as the No. of successes divided by the No. of attempts, will be confirmed by direct visualization.
- Representative images of the accessed anatomic landmarks will be recorded.
- Level of prior resection will be recorded – anterior or posterior ethmoidectomy, draf IIa, draf IIb, uncinatectomy, antrostomy, maxillectomy, sphenoidotomy, dilation

Secondary - Performance

- Image quality – will be assessed through a yes/no statement regarding adequacy of Peregrine image quality for office endoscopy procedures, in comparison to the comparison device.
- Patient pain and tolerability will be assessed through validated VAS for both Peregrine and the comparison endoscope.
- Impact of Peregrine's extended visualization capability on clinical workflow will be evaluated through a series of questions regarding identification of pathology, evaluation of mucosa, change in medical management, need for additional CT scan, indication for revision surgery, etc.
- Peregrine ease-of-use will be evaluated through a user questionnaire.

Other Measurement – Performance and effectiveness

- Irrigation (through Peregrine working channel) will be documented (performed/not performed), when performed.
- To evaluate nasal cavity inflammation and sinuses inflammation using Lund Mackay CT score and Lund Kennedy Endoscopic scoring, if applicable.

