6 INVESTIGATION PLAN

6.1 Study Design

Type of Study

This is an open, single-center, prospective study in which the investigational device, the Peregrine Drivable ENT Scope, will be tested in a single group of adult patients, male or females.

The rationale behind this study is to show that the ability to visualize intra-sinus anatomic landmarks of the Maxillary, Frontal and Sphenoid sinuses is comparable to or better than the ability to visualize them with a Standard 70° 4mm Endoscope in the office setting; This study will evaluate the safety and performance of the Peregrine endoscope which enables intra-sinus visualization as a first step to assess potential benefits, such as minimizing CT scans and associated radiation exposure, change in medication regimen, referral to revision surgery, saving multiple office visits, and cost.

This study is proposed after completing a series of clinical cases with the Sinusway endoscopy system, (which is similar to the Peregrine Endoscopy system) which demonstrated that the system is safe and performed well to physician's satisfaction (detailed information on the studies is provided in the Investigator's Brochure).

Measures to Minimize Bias

Subjects shall constitute their own control group by comparing the ability to visualize intra-sinus anatomic landmarks and pain and tolerability between Peregrine and a standard endoscope in the same subject. For this reason, no randomization is necessary in this study.

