7 STATISTICAL CONSIDERATIONS AND SAMPLE SIZE

Statistical Considerations

Demographic and baseline characteristics will be summarized for all subjects included in the analysis. Continuous variables will be summarized using summary statistics (mean, standard deviation, median, range combined with 95% confidence interval calculations) and categorical variables will be summarized using counts and percentages.

In particular, the following tests according to the parameters type are going to be performed:

- Continuous parameters will be presented by the estimated value and calculation of 95% confidence intervals. In addition, the comparison will be by using the relevant Student's t-test.
- Categorical parameters will be analyzed by Fisher exact test/ chi-square tests (in case of low observed frequencies).

Tests will be two-sided in accordance to the hypothesis regarding the tested parameters, with a significance level of 0.05.

Sample Size

Up to thirty (30) patients are expected to complete the study.

The primary endpoint of the study will be to demonstrate that the Peregrine Endoscope will perform comparable to or better than a Standard 70° 4mm Endoscope, where a difference of 20% or more between visualization success rates will be considered to be statistically significant. Per protocol, a subgroup analysis of each of the different sinus cavities (i.e., Frontal, Maxillary and Sphenoid) will be used for power calculation.

In order to maintain minimal Power 80% and Type I ($=\alpha$) error of 5% to detect minimal differences of $\pm 20\%$, a sample size of 7 samples is needed per sinus cavity. This number does not include an estimated 20-30% drop-out rate due to technical reasons unrelated to the device. Therefore, a sample size of 10 samples per each sinus cavity, and a total of 30 samples for all sinuses (total of up to 30 patients), will be recruited to the study.

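### Seven samples per sinus cavity do not give 80% power for a 20-point difference, and the rule that calls such a difference statistically significant conflicts with the 5% level

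*Combined protocol and SAP*

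**What the plan says.** The sample-size text appears twice, in the synopsis (Sample Size Calculations) and in Section 7 (Sample Size). Both say "a sample size of 7 samples is needed per sinus cavity" to achieve 80% power with 5% type I error for a ±20% difference in visualization success rate, calculated separately for the frontal, maxillary and sphenoid sinuses. Both raise 7 to 10 for 20–30% drop-out. The synopsis (Study Procedures) asks for "at least 10 samples per each of the frontal, maxillary and sphenoid sinuses".

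Both texts also state that "a difference of 20% or more between visualization success rates will be considered to be statistically significant".

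On the analysis, Section 7 says "Categorical parameters will be analyzed by Fisher exact test/ chi-square tests (in case of low observed frequencies") and "Tests will be two-sided in accordance to the hypothesis regarding the tested parameters, with a significance level of 0.05". Section 4.3 defines the endpoint as "Visualization success rates, calculated as the No. of successes divided by the No. of attempts" and lists four landmarks per sinus, without saying whether an attempt is a landmark or a sinus. Section 6.1 makes the comparison within patient: "Subjects shall constitute their own control group by comparing the ability to visualize intra-sinus anatomic landmarks".

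**The concern.** Seven binary observations carry very little information about a 20-point difference between two rates, and nothing in the plan explains how 7 was obtained.

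Two things are at stake. First, the aim is to show that Peregrine performs at least as well as the standard scope. If the comparison has almost no power, a non-significant result in a cavity is the usual outcome even when Peregrine is 20 points worse, and the stated 80% invites readers to take it as evidence of comparability. Second, statistical significance is set by the test and the 0.05 level, not by a fixed size of difference. If the 20% rule were applied to observed gaps, it would replace the 5% error rate with a different and usually much larger one.

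**Working it through.** **Inputs.** From Section 7: n = 7 per cavity (10 recruited), two-sided 0.05, 80% power, a 20-point difference, Fisher or chi-square. From Section 6.1: both scopes in the same patient. The plan gives no success rates or discordance, so I assume every pair of rates 20 points apart, from 0% vs 20% to 80% vs 100%, and one success/failure per sinus unless stated otherwise.

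**1. Trying to reproduce 7.** The usual two-proportion formula, with p̄ the mean of the two rates, is

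n = [1.96·√(2p̄(1−p̄)) + 0.84·√(p₁(1−p₁) + p₂(1−p₂))]² / 0.20²

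It gives 35 per scope at 80% vs 100% and 97 at 40% vs 60%. The smallest one-sided value, without continuity correction, is 27. A two-sided one-sample test needs at least 16. None gives 7. The drop-out step does reproduce: 7/0.7 = 10.

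**2. Exact power.** For each base rate p, sum Bin(a; n, p) × Bin(b; n, p + 0.20) over all outcomes (a, b) with two-sided p ≤ 0.05. For exact McNemar, sum the multinomial over discordant pairs, with discordance from 20%/0% to 60%/40%.

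| True 20-point difference | n = 7 | n = 10 |
|---|---|---|
| Fisher | 0.5–4.0% | 3.3–6.0% |
| Chi-square, uncorrected, pairing ignored | 3.3–12.8% | 12.1–14.4% |
| Exact McNemar | 0.04–3.7% | 0.6–5.8% |

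One case can be checked by hand. At 80% vs 100% with n = 7, the better scope always scores 7/7. Fisher then needs 2/7 or fewer from the other: P(Bin(7, 0.8) ≤ 2) = 0.0047. Chi-square needs 3/7 or fewer: 0.033.

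At n = 10 the best figure is 14.4%, so a true 20-point difference is missed at least 100 − 14.4 = 85.6% of the time.

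**3. What these sizes can detect.** For a one-way difference d, exact McNemar needs at least 6 discordant pairs, all in one direction. P(Bin(n, d) ≥ 6) reaches 80% at d of about 88 points for n = 7 and 67–68 points for n = 10. At d = 50 points and n = 10 it is 38%.

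**4. Can an observed 20-point gap be significant?** Smallest attainable p-values:

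| Observed gap | Chi-square | Fisher | Exact McNemar |
|---|---|---|---|
| 2/10 (20 points) | 0.136 | 0.474 | 0.50 |
| 2/7 (28.6 points; 20 points cannot occur at n = 7) | 0.127 | 0.462 | 0.50 |

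At either size, significance needs a gap of at least 4 successes (chi-square), 5 (Fisher) or a net 6 (McNemar).

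**5. Error rate if the 20% rule is applied to observed gaps.** With equal true rates and n = 10, the chance of an absolute gap of 2 or more is 11% at 95%, 24% at 90%, 39% at 80% and 50% at 50%. In paired form it is 12% at 5%/5% discordance and 50% at 25%/25%.

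**6. More favourable readings.**

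- *Landmarks as independent units.* 7 × 4 = 28: Fisher 22–50%, chi-square 31–84% (84% at 80 vs 100, 60% at 75 vs 95, 47% at 70 vs 90), exact McNemar 13–50%. 10 × 4 = 40: Fisher 37–84%, chi-square 46–97%, exact McNemar 19–84%. All ignore clustering of landmarks within a sinus.
- *Paired t-test on the fraction of landmarks seen.* 80% at n = 7 needs a standard deviation of differences of 0.157 or less. At 0.20, power is 60% (n = 7) and 80% (n = 10); at 0.40 it is 20% and 29%.
- *One-sided non-inferiority, margin 0.20, unpaired.* n = 6.18 × [p₁(1−p₁) + p₂(1−p₂)] / (p₂ − p₁ + 0.20)², where 6.18 = (1.645 + 0.842)². Both rates 98%: 6.06, so 7. Standard 80%, Peregrine 100%: 6.18, so 7. Both 95%: 15. Both 90%: 28. Both 80%: 50.

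**The case against.** The strongest reply is that one binary result per sinus is not the only reading, nor clearly the intended one. The endpoint is built on four landmarks per sinus. On landmark counts power is higher, and a gap near 20 points can reach significance. That is correct, and the headline figures hold only under the per-sinus condition. But at 28 landmarks only chi-square passes 80%, and only near 80% vs 100%, with landmarks of the same sinus treated as independent.

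A second reply is that the aim reads like non-inferiority and the data are paired, so the relevant quantity is discordance, not the marginal rates. The paired formula is n = 6.18 × [(b + c) − (b − c)²] / (b − c + 0.20)², where b and c are the shares seen only by Peregrine and only by the standard scope. It gives 6.96, so 7, for equal rates with 4.5% total discordance, and 16 at 10%. If the standard scope never sees what Peregrine misses, it gives about 7 or fewer. So 7 can arise under more assumptions than the unpaired formula suggests. None of them is in the plan, the approximation is weak at n = 7, and Section 7 specifies two-sided tests.

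Third, the 20% rule may be loose wording for the difference to be detected, and if both true rates are very high its error falls: 5.2% at 97% and 2.7% at 98%. That stands, but the rule as printed still conflicts with the 0.05 level over most of the range.

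Last, the synopsis's minimum wording makes 10 a possible floor. The n = 10 figures apply if about 10 per cavity are obtained, which is what the sample-size text plans.

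**Conclusion.** The concern holds. The plan gives no inputs that produce 7. With one success/failure result per sinus and the two-sided tests it names, power for a true 20-point difference is at most 12.8% at 7 and 14.4% at 10, against a stated 80%. This is true at every base rate, so the missing rate cannot rescue it; exact McNemar is no better. Readings that reach 80% at 7 need unstated inputs: independent landmarks at near-ceiling rates, a standard deviation of 0.157 or less, or one-sided non-inferiority with very few discordant sinuses or an assumed Peregrine advantage.

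At the per-sinus level, the 20% significance rule contradicts the 0.05 level. A 2/10 gap cannot be significant under any of the three tests, and acting on it would carry an 11–50% false-positive rate for equal true rates between 95% and 50%.

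Both statements concern the primary performance endpoint and should be corrected before the results are interpreted.

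**What to change.** In the synopsis and in Section 7:

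1. Delete the claim that 7 samples give 80% power.
2. Delete the rule that a difference of 20% or more counts as statistically significant.
3. State what one sample is. If landmarks are analysed, say that they are clustered within sinus and patient.
4. Describe 10 sinuses per cavity as a feasibility size and give its precision; for example, the exact 95% confidence interval for 8/10 is 44.4% to 97.5%.
5. Report the per-cavity paired differences as estimates with 95% confidence intervals, and state that a non-significant result is not evidence of comparability.

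If non-inferiority is intended, state the margin, the sidedness and the expected rates. If a detectable difference is quoted (about 67–68 points one-way at n = 10), name exact McNemar as the paired analysis.

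The cost is wording in two places, with no extra patients or procedures. The price is candour: the stated power becomes far less favourable, and the per-cavity comparison becomes an estimate instead of a powered test.

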8 RISK ANALYSIS

Risk analysis for the Sinusway device has been conducted as part of FDA 510k submission (K162916). The Risk analysis was revised following the modification applied to the Peregrine endoscope. This risk analysis is applicable to the proposed clinical investigation. The potential risks described below will be explained to the subject in the informed consent process. Risk and Benefits summary of the investigational device will be presented in the Investigator's brochure.

8.1 Potential risks – (Peregrine):

Endoscopy is a minimally invasive, diagnostic medical procedure (4). Overall, nasal endoscopy is a safe and low risk procedure. Occasionally, gagging, nosebleeds or coughing may occur as the endoscope is threaded through a nostril (5). Mucosal trauma and bleeding may rarely occur, particularly in susceptible patients with increased risk of bleeding, such as those receiving aspirin or other anticoagulant medications (i.e. Plavix®, Coumadin®, etc.). In addition, although not related to the endoscopic devices, adverse reactions to the topical decongestants or anesthetic provided prior to the procedure may occur prompting verification of patients' allergies prior to application

8.2 Definitions of Adverse Device Events and Adverse Events

Adverse Device Effect (ADE)

- An "Adverse Device Effect" is an adverse event related to the use of an investigational medical device.
- This includes any adverse event resulting from insufficiencies or inadequacies in the instructions for use, the deployment, the installation, the operation, or any malfunction of the investigational medical device.
- This includes any event that is a result of a use error or intentional misuse.
- "Adverse Events" are defined as any untoward medical occurrence, unintended disease or injury or any untoward clinical signs (including an abnormal laboratory finding) in subjects, users or other persons whether or not related to the investigational medical device.
- This includes events related to the investigational device.
- This includes events related to the procedures involved (any procedure in the clinical investigation plan).
- For users or other persons this is restricted to events related to the investigational medical device.
- All Adverse device effects must be recorded in the CRF. A description of the event, including the start date, resolution date, action taken, and the outcome should be provided.

All adverse events will be graded for severity as follows:

Grade	Degree	Description
1	Mild	Symptom(s) barely noticeable to patient or does not make patient uncomfortable; does not influence performance or functioning; prescription drug not ordinarily needed for relief of symptom(s) but may be given because of personality of patient.
2	Moderate	Symptom(s) of a sufficient severity to make patient uncomfortable; performance of daily activity is influenced; patient is able to continue in study; treatment for symptom(s) may be needed.
3	Severe	Cause severe discomfort; symptoms cause incapacitation or significant impact on patient's daily life; severity may cause cessation of treatment with study device; treatment for symptom(s) may be given and/or patient hospitalized.
4	Life-threatening	May result in death if not promptly treated and reversed.
5	Fatal	Results in death

Relationship -whether or not the test procedure/device caused the adverse event

Degree	Description
Definitely	There is evidence of exposure to the test procedure/device , the AE is most likely to be explained by the test procedure / device than by another cause; the challenge is positive; rechallenge (if feasible) is positive; the AE shows a pattern consistent with previous knowledge of the test procedure / device.
Probably	There is evidence of exposure to the test procedure / device; the temporal sequence of the AE onset relative to the test procedure / device is reasonable; the AE is more likely explained by the test procedure / device than by another cause.
Possibly	There is evidence of exposure to the test procedure / device; the temporal sequence of the AE relative to the test procedure / device is reasonable; the AE could have been due to another equally likely cause;
Probably not	There is evidence of exposure to the test procedure / device; there is another more likely cause of the AE
Definitely not	The patient did not receive the test procedure / device; or temporal sequence of the AE onset relative to test procedure / device is not reasonable; or there is another obvious cause of the AE.

Action taken - whether or not the adverse event caused the subject to be discontinued from the study.

Clinical Outcome – whether the adverse event was resolved or ongoing.

All adverse events, including a worsening of physical examination findings, in comparison with baseline values, must be followed until the event resolves, the condition stabilizes, the event is otherwise explained, or the patient is lost to follow-up.

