4.1 Safety assessment

Safety assessment will be based upon monitoring the adverse device effects, which will be collected throughout the procedure.

All adverse events and serious adverse events will be reported in accordance with reviewing Ethics Committee /Institutional Review Board (IRB), FDA and Competent authority requirements.

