4. Obligatory – the surgeon will then attempt to visualize the pre-defined sinus anatomy landmarks with Peregrine endoscope which will be recorded as success/failure, and an image of the anatomic landmarks visualized will be taken. Patient will be asked to score Peregrine for pain and tolerability.
5. Optional – the surgeon will have the option to attempt to visualize the pre-defined sinus anatomy landmarks with a standard 70° 4mm endoscope and/or a flexible endoscope which will be recorded as success/failure, and an image of the anatomic landmarks visualized will be taken. Patient will be asked to score the endoscope for pain and tolerability.
6. Optional - irrigation of the nasal anatomy will be performed and recorded as Done/Not Done and which sinus was irrigated.
7. The physician will answer a set of questions related to endoscope usability and utility in clinical decision making in comparison to the standard endoscope.
8. The procedure will be recorded by site's AIDA system to enable the physician to perform assessments post procedure.

- **After the procedure:**

- The patient will recover from the procedure according to center's common practice. Before the patient is dismissed, recording of AE, if any, will be performed. Patient will exit the study.

Visit 3: Telephone Follow-up visit

- Telephone Follow-up for safety assessment will be conducted by study personnel two weeks \pm 3 days following patient last study visit.
- In the absence of any on-going ADE's, the patient will exit the study and Exit Form will be completed.

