6.3 Methods and Timing for assessments

Schedules of assessments are listed in **Table No. 1 below**.

Table 1: Study visit schedule

Study Activities	Visit I: Screening and Inclusion	Visit II: Procedure At day of screening or within 30 days post screening	Visit III: Telephone Follow-up Up to 2 weeks ± 3 days from visit II
Informed Consent	X		
Demographic Data	X		
Medical History	X		
SNOT 22	X		
Concomitant medication related to sinus disease	X		
Physical Examination	X		
Vital Signs (optional)	X		
Inclusion/exclusion criteria	X		
CT scan (as available)	X (optional)		
Lund Mackay/Kennedy inflammation score	X		
Endoscopy with Peregrine and a standard Endoscope		X	
User questionnaire		X	
Patient tolerability and pain score		X	
AEs/SAEs		X	X
Patient Exit			X

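### Clinical signs count as adverse events, but after Peregrine no mandatory examination or prompted mucosal finding is planned, so silent or minor mucosal injury may go unrecorded or be unattributable to one scope

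*Combined protocol and SAP*

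**What the plan says.** The synopsis lists device-related adverse events as a primary endpoint. Section 4.3 says: "All adverse device effects will be captured and summarized as defined in" Section 8, and expects type, frequency and severity to resemble the published experience. It adds: "For this study, the Safety comparison with the data of Nasal Endoscopy reported in the literature will be descriptive with no statistical endpoints".

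Section 8.2 defines adverse events to include injuries and clinical signs as well as symptoms. Its closing paragraph reads: "All adverse events, including a worsening of physical examination findings, in comparison with baseline values, must be followed" until they resolve, stabilise or are otherwise explained, or the patient is lost. Section 8.1, on the potential risks of Peregrine, says: "Mucosal trauma and bleeding may rarely occur, particularly in susceptible patients with increased risk of bleeding".

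On how events are found, Section 4.1 says: "Safety assessment will be based upon monitoring the adverse device effects, which will be collected throughout the procedure". Section 8.6 makes the investigator responsible for documenting all device-related events and has them recorded from admission at Visit 2. Section 6.2 has adverse events recorded before the patient leaves, and then: "Telephone Follow-up for safety assessment will be conducted by study personnel two weeks" (± 3 days) after the last study visit. In Table 1 (Section 6.3) the row "Physical Examination X" has its single mark under Visit I, as does the Lund Mackay/Kennedy row. Section 6.2 step 8 says: "The procedure will be recorded by site's AIDA system to enable the physician to perform assessments post procedure".

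**The concern.** A rule that treats worsening from baseline as an adverse event needs a later finding to set against the baseline. The schedule supplies the baseline and no required later value. The missing observation concerns the injury that the plan itself names as a device risk, in a nose under local or topical anaesthesia, where a small lesion may cause no symptom for the patient to report in the clinic or by telephone.

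Because the safety comparison is descriptive, its worth depends on how events are found. If minor injury is recorded only when the operator happens to note it, a low or zero count reflects recording practice as well as the device. Attribution is also at stake: Section 8.2 asks for a judgement of relationship to the test procedure or device, and two scopes are passed in the same session.

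**Working it through.** The plan sets no statistical target for safety, so there is no figure of its own to reproduce. The check is a cross-reading, followed by a short illustration.

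**Opportunities to find an injury from Peregrine onward (Sections 6.2 and 6.3)**

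| Opportunity | Mandatory? | Mucosal finding requested? |
|---|---|---|
| Step 4, Peregrine endoscopy | Yes | No: landmark success/failure, image, pain and tolerability |
| Step 5, 70° or flexible scope | No | No: same items |
| Step 6, irrigation | No | No: done/not done and which sinus |
| Step 7, physician questions | Yes | No safety item: usability and clinical decision making |
| Step 8, video | Recorded | No safety reading assigned |
| Before leaving the clinic | Yes | Unprompted adverse event recording |
| Visit 3 | See below | Telephone, so no examination |

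The direct view at step 4 exists, and anything seen there is reportable under Sections 4.1, 8.2 and 8.6. No step asks the operator to look for a lesion or to record that none was present.

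**Baseline.** Table 1 lists a physical examination at Visit I, but the Visit 1 list in Section 6.2 omits it. The Lund scores are not repeated after the procedure.

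**Attribution.** Step 3 (30° scope) always precedes step 4 (Peregrine), and no mucosal finding is recorded between them. A lesion seen during or after step 4 could predate the session or come from either scope.

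**Visit 3.** Section 6.2 has the patient exit after the procedure, then describes the telephone call and a second exit. Table 1 places exit at Visit III. The synopsis lists Visits 1 and 2 only. These passages must be reconciled.

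**Illustration.** Inputs: n = 30 (Section 7, the maximum); true per-patient rate p and detection proportion s, both assumed because the documents give neither; patients independent. Expected recorded events = 30 × p × s. Chance of recording none = (1 − p × s)^30.

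| p | Expected, s = 1 | None, s = 1 | Expected, s = 0.5 | None, s = 0.5 |
|---|---|---|---|---|
| 1% | 0.30 | 0.99^30 = 74% | 0.15 | 0.995^30 = 86% |
| 2% | 0.60 | 0.98^30 = 55% | 0.30 | 0.99^30 = 74% |
| 5% | 1.50 | 0.95^30 = 21% | 0.75 | 0.975^30 = 47% |
| 10% | 3.00 | 0.90^30 = 4% | 1.50 | 0.95^30 = 21% |

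With 0 events in 30, the one-sided 95% upper bound on the true rate is 1 − 0.05^(1/30) = 9.5% if detection is complete, and 9.5% / 0.5 = 19.0% if half of events are detected.

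**The case against.** The strongest reply is that the main safety capture is the procedure itself. Device effects are collected throughout, the surgeon sees the mucosa through Peregrine, clinical signs count without symptoms, and the investigator must document what is device-related. This stands: overt trauma or bleeding would probably be noticed and is reportable. A reader might infer that the plan can register only symptomatic events, or that nobody looks after Peregrine enters. The documents do not support either reading, and an optional 70° or flexible look may follow as well.

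The sentence on worsening in Section 8.2 is also a rule about how long events are followed. It implies that worsening counts as an adverse event, but it does not promise a repeat examination. The point is therefore a mismatch between definition and schedule, not a scheduled examination that was left out.

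On size, Section 8.1 says that mucosal trauma and bleeding occur rarely, and Section 8.4 calls minor complications uncommon. At rates of 1% or 2%, a zero count is more likely than not even with full detection, so the number of patients is the main limit. A reader might take a steep contrast at 10% as the expected effect; the documents support neither that rate nor any particular detection proportion.

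Finally, no decision rule turns on the count, and if the published series relied on routine observation, prompted recording would make the comparison less like-for-like. That is fair, and it is a reason to report the two kinds of event separately. None of this supplies a prompt for minor lesions or a finding between the two scopes.

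**Conclusion.** The point holds in a limited form. For a primary endpoint, the plan counts signs and worsening from baseline as adverse events, but after Peregrine it requires no examination and prompts no mucosal finding. What is exposed is silent or minor injury that nobody is asked to record, and injury that cannot be assigned to one scope. Events that the surgeon notices are already covered.

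The size cannot be estimated from the documents. Under the stated assumptions, halving detection raises the chance of a zero count from 55% to 74% at a 2% rate, and from 4% to 21% at 10%. These figures are illustrative; the mismatch in the text does not depend on them. The correction is worth making because it is nearly free and bears on a primary endpoint. The gap does not leave patients without safety monitoring.

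**What to change.** - In Section 6.2 steps 3 and 4, have the surgeon record mucosal trauma and bleeding as present or absent, with site, as seen on withdrawal of the 30° scope before Peregrine is inserted, and again on withdrawal of Peregrine. Name the step 8 recording as source.
- Add this finding to the Visit II safety row of Table 1 and report it by scope.
- Count a lesion as new after Peregrine only where the same site was seen without it on the 30° view. Otherwise report it as not assessable for change, since Peregrine may show areas that the 30° scope does not.
- Leave the Section 8.2 definition of adverse events as it is, so that later findings still count. Do not rely on its severity grades for silent signs: they are written in terms of symptoms, and such a sign fits at most grade 1.
- Report prompted and unprompted events separately.
- Reconcile the exit and Visit 3 wording in Section 6.2 and Table 1 with the synopsis.

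The cost is two CRF items, short additions to Section 6.2 and Table 1, and a reporting rule. No procedure or staff is added, because both scopes are withdrawn and the session is recorded anyway. The downside is that the count of minor mucosal events will probably rise and may be less comparable with literature based on routine observation; the separate reporting addresses this.
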